7.5 Baseline Data

All observations available prior to the operative date will be defined as baseline (or preoperative) data. All demographic and pre-operative characteristics data will be summarized at baseline. All demographic (including age categorised whether "<65" and "≥65") and baseline characteristics will be summarized by surgical method (with or without Patella Resurfacing) using the SAF analysis populations.

All data under below forms will be summarized for screening: Demographics Vital Signs Subject Pregnancy

Whether a subject has relevant medical history and/or diseases or past surgery will be summarised, and the average number per subject summarised. Details provided in a listing of medical history term, start/end date and ongoing.

All data under below forms will be summarized for Operative Details: Operative Data

Device IDs will be provided in a listing.

7.6 Disposition Data

A table will be provided summarising number of subjects.

Subject (and knee) disposition will be summarized after completion of the study using frequency (n) and percentage (%) of subjects (or knee) who completed and who did not complete the study. For those who did not complete the study, the primary reason for discontinuation will additionally be summarized.

CONFIDENTIAL AND PROPRIETARY

Statistical Analysis Plan

A Prospective Multi-Centre Study in Patients Undergoing Total Knee Replacement with JOURNEY II CR Total Knee System Number: Journey II

CR.2020.11 ST: ST1197

Version: V1.0, 20-MAY-

2024

Page: 16 of 20

The number of knees that enter the study, and the number of knees with follow up information will be provided by visit:

- Theoretically due: number enrolled and implanted with study device
- Deaths: cumulative number of subjects that died prior to the study visit
- Revisions / failures: cumulative number of subjects that revised/failed prior to the study visit
- Cumulative terminations: terminated from study other than from revision or death
- Expected = theoretical due cumulative (deaths + revisions + termination)
- Actual = actual number of subjects at follow up visit
- Follow up = actual / expected x 100.

The number of subjects that have discontinued from the study and reasons for withdrawal will be summarised.

Study duration and the duration between surgery and each visit will be summarised.

Screening and enrolment summary: For each centre/site, dates that the first subject was screened/enrolled and the last subject completed will be provided, duration (site, 1st enrolled – final subject exit), together with number of subjects enrolled and number of subjects completed 10 year visit.

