6.3 Interim Analysis

The protocol stated an interim analysis was planned after the 2 year visit. However due to premature termination of the study no interim analyses will be performed.

7 STATISTICAL ANALYSIS 7.1 General

Smith+Nephew's Global Biostatistics group will conduct the statistical analysis for this study. Unless otherwise stated, all significance tests and hypothesis testing will be two-sided, performed at the 5% significance level. Resulting p-values will be quoted and 95% two-sided confidence intervals will be generated where appropriate. All p-values will be rounded to three decimal places, p-values less than 0.001 will be presented as '<0.001' in all tables.

Where data summaries are specified, categorical and ordinal variables will be summarized with frequencies and percentages. Continuous variables will be summarized with the following summary statistics: number of observations, mean, median, standard deviation, minimum and maximum values. All analyses will be performed in SAS 9.4 (or later).

All table summaries will be provided overall, and by surgical method (resurfaced/un-resurfaced patella).

Example mock shells are provided below:

Table: Demographics by subject				
		Resurfaced Patella	Un-Resurfaced Patella	Overall
Age	Mean			
	Median			
	Std			
	Min			
	Max			
	Q1			
	Q3			
	Inter Quartile Range			
	N			
Age	<65			

CONFIDENTIAL AND PROPRIETARY

Statistical Analysis Plan

Number: Journey II

CR.2020.11 ST: ST1197

Version: V1.0, 20-MAY-

2024

Page: 9 of 20

A Prospective Multi-Centre Study in Patients Undergoing Total Knee Replacement with JOURNEY II CR Total Knee System

>=65		
N		

PROM by knee				
Assessment		Resurfaced Patella	Un-Resurfaced Patella	Overall
Pre-Operative	Mean			
	Median			
	Std			
	Min			
	Max			
	Q1			
	Q3			
	Inter Quartile Ran	nge		
	N			
6 Month				
1 Year				
2 Year				
3 Year				

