Any revisions, and detail of, will be provided in a listing.

If feasible based on data available at premature termination, Kaplan Meier estimates and 95% confidence intervals will be provided by surgical method. Knees implanted without an on-study revision will be censored on the date of their last known follow-up visit. Any premature knee discontinuation from study due to a subject's death or for any other reason, excluding lost-to-follow-up, will be censored on the date of this discontinuation. Cumulative implant survivorship also be graphically illustrated.

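### SAP 7.6 counts site completers at a 10-year visit that the study does not have, and its follow-up rate needs one stated rule for revised knees and one counting unit

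*SAP*

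**What the plan says.** SAP 7.6 Disposition Data introduces the follow-up table in knees: "The number of knees that enter the study, and the number of knees with follow up information will be provided by visit". Its rows are then defined as follows.

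- The starting number has no unit: "Theoretically due: number enrolled and implanted with study device".
- Deaths are a cumulative number of subjects.
- Revisions are also in subjects, without separating types: "Revisions / failures: cumulative number of subjects that revised/failed prior to the study visit".
- Terminations are those for reasons other than revision or death, again with no unit.
- The denominator is "Expected = theoretical due cumulative (deaths + revisions + termination". The minus sign is missing in the text available to us, probably from PDF conversion, and is not counted as an error.
- The numerator is "Actual = actual number of subjects at follow up visit", and the follow-up rate is actual over expected, times 100.

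The site summary at the end of the same section asks for the "number of subjects completed 10 year visit".

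On the protocol side, 7.8.2 says that subjects whose prosthesis is revised continue follow-up visits and that later data are shown separately as safety data. After a minor revision, where only part of the implant is replaced, the subject stays on the study schedule and the data are presented. Protocol 8.1 sets follow-up at 36 months, 9.1.8 makes the 3-year visit the exit visit, and the schedules in both documents stop there.

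**The concern.** All testing has been dropped after early termination (SAP 7.10, 7.11 and 7.15), and data are analysed as observed (SAP 7.3). A reader of the final report will therefore judge the descriptive results partly by how complete follow-up was at each visit, and this table is the SAP's by-visit measure of that.

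Three things stand in the way. The site-level completion count refers to a visit that does not exist. The rate, taken at its word, can remove a revised knee from the denominator and still count it in the numerator. And the rows do not share a unit, so two programmers could build different tables from the same text. The stake is the accuracy of the disposition report; the OKS estimates do not depend on it.

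**Working it through.** **1. Completion visit.** The SAP 7.6 site summary uses 10 years. Against that stand follow-up of 36 months (Protocol 8.1), the exit visit at 3 years (Protocol 9.1.8), the last schedule column at 3 years (SAP 3) and a total study duration of 4.5 years (Protocol synopsis). No subject can complete a 10-year visit, so the count is zero or empty at every site. This needs no assumption.

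**2. Revisions.** The documents give no follow-up percentage to reproduce and no revision count. For scale, take one planned cohort: 192/(1 − 0.20) = 240 knees, which matches SAP 6.1. Assume r revised knees, no deaths or terminations, and every knee attending, revised ones included. The literal rule gives 240/(240 − r):

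| r (assumed) | Rate as written |
|---|---|
| 0 | 240/240 = 100% |
| 1 | 240/239 = 100.4% |
| 5 | 240/235 = 102.1% |
| 10 | 240/230 = 104.3% |

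If the same knees are treated alike in both counts, full attendance always reads 100%. With r = 5, this is 240/240 if all five are minor and stay in, or 235/235 if all five leave the study data and are taken out of both counts.

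**3. Units.** Let b be the share of subjects with two study knees, a figure the documents do not give. If the starting number is in knees and Actual is in subjects, full attendance with no events reads 1/(1 + b):

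- b = 0: 100%, no effect.
- b = 0.10: 100 subjects have 110 knees, and 100/110 = 90.9% overall.

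The cohort columns need not show the same shift. SAP 7.1 states "All table summaries will be provided overall, and by surgical method". If each of those 10 subjects has one knee in each cohort, subjects equal knees within a cohort, so both cohort columns read 100% while the overall column reads 90.9%. If instead the starting number is in subjects, the ratio has one unit, but the table does not deliver the knee counts it announces.

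The SAP does treat the two units as distinct. Its mock shells in 7.1 show demographics by subject and PROMs by knee, and the revision analysis in 7.11 is by knee: "Knees implanted without an on-study revision will be censored on the date of their last known follow-up visit".

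**The case against.** The strongest reply concerns revisions. The terminations row covers exits other than by revision or death, which suggests that the revisions row is also meant as an exit category. On that reading a minor revision, which stays on schedule, is not subtracted. Contacts after a full revision, whose data are no longer study data, need not count as attendance either, so numerator and denominator agree. This stands as a possible reading, and subtracting full revisions is defensible in itself. The SAP does not state the rule, however: the revisions row makes no distinction by type, and Actual has no exclusion.

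On units, Protocol 8.5.1 speaks of up to 480 subjects, the same figure as the 480 knees, which points towards one knee per subject. The word subjects in the rows may simply be loose wording for knees. Against that, data are collected by knee (Protocol study schedule, footnote 1), SAP 7.6 itself reports disposition by subject and by knee, and neither the inclusion nor the exclusion criteria rule out bilateral cases. The question stays open.

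On the 10-year visit, SAP 7.6 separately summarises completers and non-completers for the study with no such reference, so completion is not lost altogether. The corrected count may also be small. The 3-year window opens at 1095 − 60 = 1035 days, and 1035 days before the SAP date of 20 May 2024 is 20 July 2021, while the protocol version in force before enrolment is dated 2 June 2021. Few subjects could have reached that window by the SAP date, unless visits continued afterwards.

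Two stronger inferences are tempting. A reader might infer that the printed rate is always too low because of the units. It is not: there is no effect without bilateral subjects, none in the cohort columns of the split case above, and the revision rule pushes the other way. A reader might also infer that, under the planned 20% attrition, the revision error would be hidden below 100%. That depends on how the 48 lost knees are recorded. If they are terminated and 5 of the 192 attending knees are revised, the literal rule gives 192/(240 − 48 − 5) = 192/187 = 102.7%, which is plainly visible.

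**Conclusion.** The point holds as a minor one, confined to descriptive disposition reporting.

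- **10-year visit:** a certain error, with a zero or empty count at every site.
- **Revisions:** on a literal reading the rate can be overstated and can exceed 100%, for example 102.1% with an assumed 5 revised knees among 240 and full attendance. A narrower reading avoids this, so the fault is an unstated rule that the literal text gets wrong against Protocol 7.8.2.
- **Units:** an inconsistency in the text that changes numbers only if some subjects contribute two study knees. The 90.9% figure rests on an assumed 10% bilateral share and a starting number in knees.

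The 240 knees are the planned cohort size. The study ended early and the documents do not give the achieved numbers, so these percentages show direction and scale only. The documents support no statement of the net direction, and none that the OKS summaries are affected.

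**What to change.** Make three changes to SAP 7.6:

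1. Replace the 10-year visit in the site summary with the 3-year exit visit, and note that early termination may leave this count small.
2. State the revision rule: subtract only revisions after which the knee's data leave the study data under Protocol 7.8.2, exclude the same knees from Actual, and keep minor revisions in both counts.
3. Use knees in every row and show subjects alongside. If any subject has two study knees, a death or termination counts for each of them.

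The cost is a short wording change and a revised table shell, with no new data and no change to any other analysis. Depending on which situations occurred, a printed percentage may move up (units), down (revisions) or not at all.

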7.7 Protocol Deviations

The frequency of protocol deviations will be summarized along with the number of subjects experiencing each.

7.8 Measurement of Treatment Compliance

Not applicable.

7.9 Multiplicity

No adjustments for multiplicity are planned for this study.

7.10 Analysis of Primary Endpoint(s)

The protocol states:

CONFIDENTIAL AND PROPRIETARY

Statistical Analysis Plan

A Prospective Multi-Centre Study in Patients Undergoing Total Knee Replacement with JOURNEY II CR Total Knee System Number: Journey II

CR.2020.11 ST: ST1197

Version: V1.0, 20-MAY-

2024

Page: 17 of 20

The primary endpoint of this study is the OKS at 2 years. If we assume the mean of OKS at 2 years for the subjects with implant JOURNEY II TKA with and without Patella Resurfaced as $\mu 1$ and $\mu 2$. The hypothesis test will be as following:

H0: μ 1 = μ 2 vs

H1: $\mu 1 \neq \mu 2$

The mean difference (μ 1- μ 2) and 95% CI will be estimated. If zero is included in 95% CI of mean difference, then null hypothesis will be accepted, which means patella resurfacing has no impact on the outcomes of JOURNEY II TKA. Otherwise if zero is not included in 95% CI of mean difference, then alternative hypothesis (H1) will be accepted, which means patella resurfacing has significant impact on the outcomes of JOURNEY II TKA. If the lower limit of 95% CI is greater than 0, which means that the subject implant with Patella Resurfaced has higher OKS at 2 years. If the upper limit of 95% CI is less than 0, which means that the subject implant with Patella Resurfaced has lower OKS at 2 years.

In addition, the mean and 95% CI of OKS at 2 years for subjects implant with and without Patella Resurfaced will be estimated separately.

At time of writing the SAP, this study has been early terminated, the study no longer has sufficient power for this hypothesis test to be relevant and it will therefore not be performed. Summary statistics, 95% CI for $\mu 1$ and $\mu 2$ would be presented.

The primary endpoint will be summarized using the SAF population only due to premature termination.

7.11 Analysis of Secondary Endpoint(s)

All secondary endpoints will be summarized using the SAF analysis population. Changes from preoperative to postoperative will not be analysed for statistical evidence of difference in PROMs

CONFIDENTIAL AND PROPRIETARY

Statistical Analysis Plan

A Prospective Multi-Centre Study in Patients Undergoing Total Knee Replacement with JOURNEY II CR Total Knee System Number: Journey II

CR.2020.11 ST: ST1197

Version: V1.0, 20-MAY-

2024

Page: 18 of 20

due to early termination of the study and resultant lack of power. Summary statistics for observed PROMs score would be presented.

Knee Society Score (KSS), Oxford Knee Score (OKS) and Forgotten Joint Score (FJS)

The KSS score, OKS score and FJS score will be summarized at the pre-operative and postoperative visits and stratified by surgical method (resurfaced/un-resurfaced) using continuous summary characteristics.

For each PROM, the absolute change from pre-operative assessment (within subject) will also be summarised.

Standard Radiographic Assessment

The presence of radiographic observations: implant loosening, implant migration, and osteolysis and all other pertinent radiographic findings (i.e. all data under form 'Quantitative Radiographic Assessment') will be summarized as counts (n) and percentages (%) by visit. These would additionally be stratified by surgical method (resurfaced/un-resurfaced). Fisher Exact or Chi-Square test will not be performed due to premature termination.

Radiolucent lines (mm) by zone and visit will be summarized using descriptive statistics for continuous variables. These would additionally be stratified by surgical method (resurfaced/unresurfaced).

Patient expectation and patient satisfaction

The patient expectation and patient satisfaction will be summarized as counts (n) and percentages (%) by visit. These would additionally be stratified by surgical method (resurfaced/un-resurfaced). Fisher Exact or Chi-Square test will not be performed due to premature termination.

CONFIDENTIAL AND PROPRIETARY

Statistical Analysis Plan

A Prospective Multi-Centre Study in Patients Undergoing Total Knee Replacement with JOURNEY II CR Total Knee System Number: Journey II

CR.2020.11 ST: ST1197

Version: V1.0, 20-MAY-

2024

Page: 19 of 20

Time to Revision

The protocol stated that: "Kaplan Knee implant revision rate will be summarized as proportions with 95% CIs estimated using exact binomial methods for two surgical methods separately."

Any revisions, and detail of, will be provided in a listing.

If feasible based on data available at premature termination, Kaplan Meier estimates and 95% confidence intervals will be provided by surgical method. Knees implanted without an on-study revision will be censored on the date of their last known follow-up visit. Any premature knee discontinuation from study due to a subject's death or for any other reason, excluding lost-to-follow-up, will be censored on the date of this discontinuation. Cumulative implant survivorship also be graphically illustrated.

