## 10.4.2 Analysis of Secondary Endpoints

Knee Society Score (KSS), Oxford Knee Score (OKS) and Forgotten Joint Score (FJS)

The KSS score, OKS score and FJS score will be summarized at the pre-operative and postoperative visits and stratified by surgical method (resurfaced/un-resurfaced) using continuous summary characteristics. For each of these scores, repeated measures Analysis of Covariance (ANCOVA) models will be used to model the change from preoperative to postoperative and surgical method (resurfaced/un-resurfaced patella). As a minimum, each model will contain a time points (pre-operative and postoperative), the investigational site and surgical method as fixed terms, subject as a random term. Pre-operative prognostic and demographic variables such as age, BMI, sex and other related factors will be introduced as covariates. These covariates will be added to the model using a stepwise approach and a covariate is retained in the final model if and only if its associated p-value ≤ 0.1. Model based means (adjusted means or Least Square Means), mean difference and corresponding standard errors associated with different time points, different surgical methods will be presented. If the p-value associated with the different time points and/or surgical methods in the model is significant (i.e. p < 0.05), then the 95% CIs corresponding to the model-based differences will additionally be presented.

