4 STUDY OBJECTIVES

The objectives of the study are listed as below,

- 1. Evaluate performance of JOURNEY II TKA in APAC patient populations
- 2. Evaluate impact of patella resurfacing on the outcomes of JOURNEY II TKA

5 STUDY ENDPOINTS 5.1 Primary Endpoint(s)

The primary endpoint for the study is defined as the OKS at 2 years.

CONFIDENTIAL AND PROPRIETARY

Statistical Analysis Plan

A Prospective Multi-Centre Study in Patients Undergoing Total Knee Replacement with JOURNEY II CR Total Knee System Number: Journey II

CR.2020.11 ST: ST1197

Version: V1.0, 20-MAY-

2024

Page: 7 of 20

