6 STATISTICAL CONSIDERATIONS

6.1 Determination of Sample Size

The sample size is established primarily using a precision of estimates-based approach for resurfaced and unsurfaced Patella cohorts separately. As a secondary concern formal statistical hypothesis testing to assess differences between the cohorts will be a possibility.

Based on an underlying assumption of standard deviation of 7.4 in OKS reported in literature (Bohm et al 2012)., a minimum of 192 knees are required, per cohort, to ensure that there is an 80% probability that a 95% confidence interval constructed around the OKS score can be calculated to within ± 1.2 units for each cohort of resurfaced and unresurfaced knees. To allow for up to 20% attrition during the data collection activity, this will be inflated to enrol a minimum of 240 knees per cohort.

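### SAP 7.11 drops inference on pre- to post-operative PROM change for lack of power; this is not demonstrated for within-knee OKS change, and an interval for improvement is lost.

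*SAP*

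**What the plan says.** Protocol 10.4.2 planned repeated-measures ANCOVA for KSS, OKS and FJS, which "will be used to model the change from preoperative to postoperative and surgical method". Time point and surgical method were separate fixed terms, with site fixed and subject random. Adjusted means, mean differences and standard errors were to be given in all cases. The 95% CI for a difference was to be added only if its p-value was below 0.05.

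SAP 7.11 replaces this: "Changes from preoperative to postoperative will not be analysed for statistical evidence of difference in PROMs", "due to early termination of the study and resultant lack of power". It still summarises the within-subject change for each PROM, but with no interval. SAP 7.15 repeats that no tests will be done and that the endpoints receive descriptive summaries only.

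Other intervals survive termination. SAP 7.10 drops the between-cohort test of 2-year OKS, also for insufficient power, but keeps a 95% CI for each cohort mean. The time-to-revision text in 7.11 keeps Kaplan-Meier estimates with 95% CIs where the data allow. The first study objective, in SAP section 4, is to "Evaluate performance of JOURNEY II TKA in APAC patient populations".

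**The concern.** The SAP gives one reason for dropping two different questions. The first is whether resurfaced and un-resurfaced knees differ. Any such difference may be a few OKS points, and a shortened study may well be too small to detect it. The second is how much a knee improves from before to after surgery. That change is paired within knee and, on the protocol's own literature summary, is of the order of 13 to 17 points on a 0 to 48 scale. A sample too small for the first question can be ample for the second.

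A confidence interval also has no power threshold to pass. If few knees have paired data, the interval is wide, and that is what a reader needs to see. The SAP accepts this for 2-year OKS and for survivorship, but not for change.

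At stake is how the study reports improvement. OKS and KSS are scheduled before surgery and at 6 months, 1, 2 and 3 years. In a study stopped early, the 6-month and 1-year visits probably hold the most data. As written, the only PROM interval is for absolute OKS at 2 years.

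**Working it through.** **1. The plan's own precision figure.** SAP 6.1 is the only sizing in the documents. Its inputs are an SD ("Based on an underlying assumption of standard deviation of 7.4 in OKS reported in literature"), a half-width ("a 95% confidence interval constructed around the OKS score can be calculated to within ± 1.2 units") and an assurance level ("to ensure that there is an 80% probability that"). The smallest n with P(t(0.975, n−1) × s/√n ≤ 1.2) ≥ 0.80, taking s from the chi-square distribution with SD 7.4, is 163 knees per cohort. The stated 192 gives 99.65% assurance, so it does not reproduce from the stated inputs. The attrition step does: 192/(1 − 0.20) = 240. Nothing below depends on 192. This sizing concerns a cohort mean; neither document contains a power calculation for change.

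**2. Inputs for within-knee OKS change.**
- Level: "all significance tests and hypothesis testing will be two-sided, performed at the 5% significance level" (SAP 7.1).
- Mean gain: +13 (manual) and +17 (sensor-assisted) at 6 months, Protocol Table 4-2. These are literature values without an SD, not planning assumptions.
- SD of change: not given. The 7.4 in SAP 6.1 is an SD of OKS. If both time points had SD 7.4, the SD of change would be 7.4 × √(2(1 − r)): 7.4 at r = 0.5 and 10.5 at r = 0. I assume a range from 7.4 to 20 to be cautious.

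**3. Power of a paired t-test on change.** The noncentrality is δ = (gain/SD) × √n on n − 1 degrees of freedom, and power = P(|T(n−1, δ)| > t(0.975, n−1)). Smallest number of independent knees:

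| Assumed SD of change | Gain 13: 80% / 90% power | Gain 17: 80% / 90% power |
|---|---|---|
| 7.4 | 5 / 6 | 4 / 5 |
| 10.5 | 8 / 9 | 6 / 7 |
| 12 | 9 / 12 | 7 / 8 |
| 15 | 13 / 17 | 9 / 11 |
| 20 | 21 / 27 | 13 / 17 |

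At 90% power the range is 5 to 27 knees. A smaller gain of 8 points with SD 12 would need 26.

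**4. Bilateral knees.** Two knees of one subject are correlated. The design effect is 1 + (m − 1)ρ. In the worst case, with every subject contributing two knees (m = 2) and ρ = 1, it is 2, and 27 knees become 54. The plan was for up to 480.

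**5. What an interval would show.** Half-width = t(0.975, n−1) × SD/√n. With SD 12:
- n = 5: 2.776 × 12/√5 = 14.9
- n = 20: 2.093 × 12/√20 = 5.6
- n = 50: 2.010 × 12/√50 = 3.4

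**6. The between-cohort contrast, for comparison.** With SD 7.4, 80% power and two-sided 5%, an assumed difference of 3 points needs 96 knees per cohort, and 2 points needs 215. The power argument is plausible here.

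**The case against.** The strongest reply is that nobody outside the study knows how many knees had paired data. The documents give neither enrolment nor follow-up at termination, and the SAP makes even its Kaplan-Meier estimates conditional on feasibility, so the authors may have expected sparse data. Surgeons chose the technique, so one cohort could be very small. With 5 paired knees and SD 12, the half-width of 14.9 exceeds a 13-point gain. This stands. A reader might infer that the power statement is false or has no valid basis, but the documents do not support that. They support only that it is not demonstrated.

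A reader might also infer that Objective 1 is left with no interval. That is wrong. SAP 7.10 keeps a 95% CI for each cohort mean of the primary endpoint, and survivorship keeps its intervals where feasible. No document names within-knee gain as the measure of Objective 1.

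Three further points have weight. The protocol promised a CI for change only when p < 0.05, although it promised mean differences with standard errors regardless, and these go too. A reader could build an approximate interval from the n, mean and SD that SAP 7.1 requires, but that would ignore bilateral knees. Finally, a test of zero gain is close to certain to reject and, without a non-implant control, says little about this device. That is a reason to leave out the p-value, not the interval.

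**Conclusion.** The point holds in a limited form. SAP 7.11 carries a power argument that suits the between-cohort contrast over to within-knee change, with no calculation and no statement of available n. For OKS, about 5 to 27 independent knees give 90% power, or up to 54 in the bilateral worst case. This rests on 6-month gains from one cited study and on assumed SDs of change from 7.4 to 20. It covers OKS only: Table 4-2 gives no pre-operative KSS and no SD, and FJS has no pre-operative assessment, so its change cannot be computed. What is lost is the interval for improvement at each visit. Whether the lost interval would have been narrow depends on the unstated number of paired knees.

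**What to change.** In SAP 7.11, remove lack of power as the reason for not analysing within-knee change. For OKS and the KSS Objective and Functional scores, report at each post-operative visit the number of knees with paired data and the mean change from pre-operative with a 95% CI, overall and by cohort. Allow for two knees in one subject, for example with a subject random effect or cluster-robust standard errors. Exclude FJS from the change summary. Keep the resurfaced versus un-resurfaced comparison descriptive, and amend 7.15 so that it permits these intervals.

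The cost is SAP wording and a few columns in a change table already planned. No new data are needed. The one small downside is that intervals may be wide where few knees have paired data.

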# 10.5 Safety Analyses

All safety data will be summarized separately for different surgical methods (resurfaced/un-resurfaced) as follows:

- Incidence of device-related re-interventions that occur on-study will be summarized as number (n) and percentages by different surgical methods and Fisher's exact test will be performed.
- Knee implant revision rate will be summarized as proportions with 95% CIs estimated using exact binomial methods for two surgical method separately. Proportion test will be performed to compare the revision rate from two surgical methods.

All safety analysis will be performed using the SAF analysis population.

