5.3 Safety Endpoint(s)

- •All adverse events (AEs) including intra-operative adverse events and complications
- Device related re-intervention
- Device Deficiencies

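### The SAP cites the protocol's exact 95% interval for the knee revision rate but does not carry it forward; the only interval left is conditional and has no width if no knee is revised

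*SAP*

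**What the plan says.** Protocol 10.5 planned two device-failure summaries.

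- Re-intervention: "Incidence of device-related re-interventions that occur on-study will be summarized as number (n) and percentages by different surgical methods", followed by Fisher's exact test. No confidence interval was planned.
- Revision: "Knee implant revision rate will be summarized as proportions with 95% CIs estimated using exact binomial methods for two surgical method separately", followed by a test comparing the two proportions.

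The SAP was written after the study had been terminated early. It treats these items as follows.

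- Section 5.3 keeps "Device related re-intervention" as a safety endpoint.
- Section 7.1 makes frequencies and percentages the default for categorical data, calls for tables overall and by surgical method, and allows 95% intervals where appropriate.
- Section 7.6 has a follow-up accounting table by visit. One line is the number implanted; another is the running count of subjects revised or failed.
- Section 7.11, under Time to Revision, reports the exact binomial interval as what the protocol had said. It then promises a listing of revisions, and after that: "If feasible based on data available at premature termination, Kaplan Meier estimates and 95% confidence intervals will be provided by surgical method".
- Section 7.13 opens with a general promise to summarise all safety data overall and by method. The specific items are adverse event classes, adverse event attributes (including details of surgical intervention) and device deficiencies. Re-intervention is not named.
- Section 7.15 states that tests are dropped because of the termination and that endpoints will be described only.

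**The concern.** An exact interval for a single proportion is an estimate, not a test. It needs no power, so lack of power is no reason to lose it. The SAP recognises this for the primary endpoint: section 7.10 drops the hypothesis test but keeps the 95% interval for each group mean. The revision rate does not get the same explicit treatment, and section 7.15 does not say why.

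What is at stake is how a low revision count will read. If a group has no revisions, the plan allows a report with an empty listing and either no Kaplan-Meier analysis or a flat curve. Without an upper limit, a reader could take a small or short study as evidence that revision is rare. Re-intervention has a related but lesser problem: with no named analysis, the numerator, the unit (knee or subject) and the table are left to whoever programs the output.

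**Working it through.** **1. Figures in the plan.** The documents state no expected revision rate, no expected re-intervention rate and no precision target for either. The sample size in SAP 6.1 concerns the OKS mean only. Its attrition step reproduces: 192 / (1 − 0.20) = 240 knees per cohort. I use 240 only as the top of an assumed range, because neither document gives the number of knees at termination.

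**2. What survives for revision, item by item.**

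| Item | Protocol 10.5 | SAP |
|---|---|---|
| Count of revisions | Implied by the proportion | Listing (7.11); cumulative count by visit (7.6), by subject, with failures included |
| Denominator | Knees, by method | Number implanted (7.6); split by method only through the general rule in 7.1 |
| Exact 95% interval | Planned per method | Cited in 7.11, not committed to |
| Other interval | None | Kaplan-Meier, conditional on undefined feasibility |
| Test between methods | Planned | Dropped, declared in 7.15 |

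**3. Kaplan-Meier with no events.** Greenwood's formula is Var[S(t)] = S(t)² × Σ dᵢ / [nᵢ(nᵢ − dᵢ)], summed over event times. With no revisions every dᵢ is 0, so S(t) = 1 and the variance is 0. The interval collapses to the single value 1. Even if the analysis is judged feasible, it gives no upper bound on the revision risk in this case.

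**4. Exact (Clopper-Pearson) interval with no events.** The two-sided 95% upper limit p solves (1 − p)ⁿ = 0.025, so p = 1 − 0.025^(1/n).

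- n = 20: 1 − 0.025^(1/20) = 16.84%
- n = 50: 7.11%
- n = 100: 3.62%
- n = 240: 1.53%

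**5. Exact interval with one event.** The upper limit is the 0.975 quantile of a Beta(2, n − 1) distribution.

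| Assumed knees per group | 0 revisions, upper limit | 1 revision, upper limit |
|---|---|---|
| 20 | 16.8% | 24.9% |
| 50 | 7.1% | 10.6% |
| 100 | 3.6% | 5.4% |
| 240 | 1.5% | 2.3% |

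The exact interval can be computed at every size in the range, including with zero events. The SAP as written guarantees none of these limits.

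**6. Re-intervention.** The protocol promised n and a percentage by method. SAP 5.3, the default in 7.1, the general opening of 7.13 and the descriptive summaries in 7.15 can together be read as still giving this. But a summary of surgical intervention details among adverse events is not a count of knees with at least one device-related re-intervention, and no section defines that count.

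**The case against.** The best defence has four parts.

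- **The interval may still be in force.** Where the SAP gives up a protocol analysis it usually says so, as in 7.10 and twice in 7.11. It says nothing of the kind after citing the exact interval, and 7.15 withdraws only tests. This is fair as far as it goes: the text is ambiguous and does not expressly withdraw the interval. But the section's own commitments are a listing and a conditional Kaplan-Meier analysis, and a programmer following them would not produce the exact interval.
- **Kaplan-Meier is a sound choice.** Early termination is likely to leave unequal follow-up, and a crude proportion ignores censoring and can understate cumulative risk. This stands. It is a reason to report both, with follow-up duration beside the proportion. It does not help when there are no events.
- **Revisions are already counted.** A reader might infer that revisions could go unreported as a rate altogether. The documents do not support that. The 7.6 table puts a cumulative count next to the number implanted, so a crude rate can be worked out. Its limits are that it counts subjects in a table introduced as counting knees, merges revisions with failures and has no interval.
- **Re-intervention has not been dropped.** A reader might also infer that the endpoint, or an upper bound for it, has been lost. Neither follows. Section 5.3 and the general rules still cover it, and the protocol never planned an interval for it. The SAP also refers to separate table shells, which are not among the documents, so a dedicated table may exist. The endpoint is under-specified, not removed.

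**Conclusion.** The point holds for revision. The planned exact 95% interval is cited but not carried forward, the remaining interval depends on an undefined condition and has no width with zero events, and the change is not declared in 7.15. For re-intervention the point is narrower: the endpoint remains, but no specific analysis is named.

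The size depends on the number of knees, which the documents do not give. Over an assumed 20 to 240 knees per group, the upper limit that would go unreported with zero revisions runs from 16.8% down to 1.5%. That few or no revisions will occur is plausible after early termination, but it is an assumption; neither document gives a count or an expected rate. The limits also treat knees as independent and take no account of differing follow-up. The primary endpoint is unaffected. This is a gap in SAP wording that is worth closing before the results are reported.

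**What to change.** In SAP 7.11 or 7.13, state without condition, for the safety population, per knee, by surgical method and overall:

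1. the number and percentage of knees revised, with an exact binomial 95% interval and no test, and a summary of follow-up duration in the same table;
2. the number and percentage of knees with at least one device-related re-intervention, as the protocol planned. An exact interval here would be an optional addition, not a restoration.

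Keep Kaplan-Meier as an addition where the number of events allows, and say what makes it feasible. In 7.15, state that for these two endpoints only the Fisher and proportion tests are dropped. In 7.6, make the revision line count knees or explain why it counts subjects.

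The cost is a few sentences and one table from data already collected. The intervals may be wide, which is a fair picture of what a terminated study can show.
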